8.3.3. Reporting Requirements

- To comply with applicable laws, regulations and standards regarding Investigator's and Institution's obligations, as the sponsor of the Study, to collect and report adverse events to regulatory authorities, IRBs, Ethics Committees or other third parties. In addition to the obligations set forth below, Investigator and Institution agree to provide Lilly with a copy of all information Investigator and/or Institution submit to regulators related to any adverse events for the Study Drug that occur during the Study that Investigator and/or Institution have not otherwise provided Lilly;
- To notify Lilly, sub-investigators, and the IRB of any problems involving risk to Study patients and report new safety information to IRBs in accordance with applicable requirements;
- to notify Lilly within twenty-four (24) hours of Investigator and/or Institution receiving notification of any "serious" adverse event experienced by a patient participating in the Study and receiving Study Drug. For purposes of this requirement, "serious" means: (1) death; (2) in-patient hospitalization or prolonged hospitalization; (3) life-threatening; (4) persistent or significant disability or incapacity; (5) congenital anomaly or birth defect; or (6) other serious events that may jeopardize the patient and may require medical or surgical intervention to prevent one of the other five listed outcomes. Serious adverse events should be reported to Lilly using a CIOMS Form or other form acceptable to Lilly. Investigator and Institution further agree to make available promptly to Lilly such records as may be necessary and pertinent for Lilly to further investigate an adverse event in the Study that is possibly associated with the Study Drug.

For SAEs which are fatal or life-threatening, unexpected, and associated with use of the study drug (Abemaciclib), a 7-Day Alert Report will be submitted to the FDA within 7 calendar days of receipt of the SAE information. For all other SAEs that are unexpected and associated with use of the study drug (Abemaciclib), a written report will be made no more than 15 calendar days from the date Eli Lilly learns of the event. Participating clinical sites will be notified of these events in parallel with FDA notification.

All AEs, including SAEs, are to be reported on the AE CRFs.

8.3.4. Recording Adverse Events in the Case Report Forms

The Investigator is to report all directly observed AEs and all AEs reported by the study patient. In addition, each study patient will be questioned about AEs. All AEs that meet the criteria specified in [Section 8.2.1](#) are to be recorded on patient source documents and on the CRFs. AEs should be reported using concise medical terminology on the CRFs.

8.3.5. Grading of Adverse Event Severity

To report AEs on the CRFs, the Investigator will use the severity grading as described in NCI CTCAE (Version 4.03). Every effort should be made by the Investigator to assess the AE according to CTCAE criteria. If the Investigator is unable to assess severity because the term is not described in NCI CTCAE (Version 4.03), then severity of MILD, MODERATE, SEVERE, LIFE-THREATENING, or FATAL may be used to describe the maximum intensity of the AE, as guided by [Table 10](#). Note that the selection of the most appropriate verbatim term for AEs is not restricted to only those toxicities represented in NCI CTCAE. For purposes of consistency, these intensity grades are defined as follows:

Table 10: Adverse Event Grading

Grade	Non-CTCAE Severity	Definition
1	Mild	Does not interfere with patient's usual function
2	Moderate	Interferes to some extent with patient's usual function
3	Severe	Interferes significantly with patient's usual function
4	Life-Threatening	Results in immediate risk of patient's death
5	Fatal	Results in patient's death

Note the distinction between the severity and the seriousness of an AE. A severe AE is not necessarily a serious AE. For example, a headache may be severe (interferes significantly with patient's usual function) but would not be classified as serious unless it met one of the criteria for serious events.

8.3.6. Relationship to Treatment Drugs (Abemaciclib)

In this study, there are 2 study drugs; the investigational drug Abemaciclib is given in combination with ADT. The relationship of each AE to each study drug will be made and

should be guided in part by the known safety profile of each drug, including the Abemaciclib IB. The relatedness should be classified by the Investigator using the following guidelines:

- Suspected Adverse Reaction: There is a reasonable possibility that study drug caused the AE (i.e., there is evidence to suggest a causal relationship between study drug and the AE).
- Not Related: There is no reasonable possibility that the AE is associated with study drug.

AEs related to study drug are considered Adverse Drug Reactions (ADR).

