2.4. Study Rationale

Recently, CDK4/6 inhibition in combination with the anti-estrogen fulvestrant was found in a randomized phase III study to prolong the progression free survival of patients with advanced hormone receptor positive, HER2 negative breast cancer refractory to previous endocrine therapy compared to fulvestrant alone, irrespective of the menopausal status of patients enrolled in the study¹. A prolonged progression free survival was also found in a randomized phase II study in combination with letrozole in the front-line setting compared to letrozole alone². Abemaciclib has demonstrated significant improvement in PFS in combination with fulvestrant and with letrozole in the MONARCH 2 and MONARCH 3 studies leading to its approval in the post endocrine therapy and also, frontline setting for hormone receptor positive, HER2 negative breast cancer ^{23,24}. The basis of this synergy involves the dependence of estrogen receptor

positive breast cancers to CDK4/6 for growth and proliferation. Additionally, activation of growth factor receptor signaling is a hallmark for endocrine therapy resistance.

A similar hormone-driven cancer akin to breast cancers is prostate cancer. These tumors are driven by androgen receptor signaling, and CDK4/6 has also been found to be a bona fide target preclinically for advanced prostate cancer cell models³. Moreover, CDK4/6 inhibition can act as a radiation sensitizer through its effects on the DNA damage response and interactions with cell cycle pathway proteins^{4,5}. For example, it has been found that expression of DNA repair proteins can be regulated by E2F, a transcription factor necessary for the G1 to S phase transition⁶. Also, cyclin D1 has been found to exert a direct role on dna repair⁷⁻⁹. Lastly, CDK4/6 inhibition has been found to modulate the DNA damage response¹⁰. These data support the use of CDK4/6 inhibitors as a modulator of DNA damage to enhance sensitivity to radiation.

Given the role of CDK4/6 in tumor resistance to endocrine therapy, in activation of the DNA damage response, and in promoting radiation resistance, we hypothesize that the targeting of CDK4/6 with abemaciclib will enhance the cytotoxicity in combination with blockade of the androgen receptor pathway. Therefore, we propose a pilot phase II investigator initiated trial in patients with high-risk prostate cancer patients testing the tolerability and toxicity of abemaciclib in combination with ADT.

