8.3.2. Adverse Event Reporting Period

Safety information for each patient will be collected from the date of informed consent. AEs occurring prior to the initiation of the study treatment with Abemaciclib study drug will be considered "baseline-emergent adverse events," will be recorded on corresponding CRFS and will not be retained for patients who fail screening. The AE reporting period for this study begins when the patient has received even a portion of the first dose of Abemaciclib study drug and ends 28 days after the last dose of the latest study treatment (i.e., Abemaciclib study drug) is administered.

All AEs that occur in study patients during the AE reporting period specified in the protocol must be reported to ELI LILLY, whether or not the event is considered study treatment-related. In addition, any known untoward event that occurs beyond the AE reporting period that the Investigator assesses as possibly related to either investigational medication/product should also be reported as an AE.

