10.2.2. Analysis of Secondary Objective

For each patient, PSA declines prior to radiotherapy- calculated from nadir level prior to initiation of radiation therapy compared from pre-treatment baseline - will be listed. The secondary endpoint will be reported as percentage of patients who achieve a PSA decline prior to radiotherapy with combination treatment of ADT and Abemaciclib compared to their baseline PSA levels. This response rate will be summarized using both a point estimate and its 2-sided 95% confidence limits.

Another secondary endpoint will be time to PSA failure. Time to PSA failure will be analyzed using the Kaplan-Meier method. SAEs (including deaths) will be tabulated. Subject listings of all AEs, SAEs (including deaths), and their attribution will be provided.

All AEs with an onset after initiation of treatment will be considered as treatment-emergent AEs. A preexisting condition that worsens after study drug treatment will also be considered as a treatment-emergent AE. All AEs will be coded by MedDRA SOC and PT.

The number and percentage of patients with the following types of treatment-emergent AEs will be summarized: all AEs, all SAEs, AEs related to study drug ((Abemaciclib), AEs resulting in study drug discontinuation, and clinically significant laboratory abnormalities. Non-treatment-emergent serious AEs will be presented separately from treatment-emergent AEs. Deaths will be reported with demographic information. Laboratory results will be summarized descriptively by dose level. Additional exploratory statistical analysis will be performed as it deemed necessary.

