 - Where possible, the visible portion of the nodal PTV should also be assessed to ensure that the associated vessels fall within the target volumes. Note that field-of-view limitations may impair ability to visualize upper aspect of the pelvis with CBCT, depending on isocenter placement
- For men receiving post-prostatectomy RT the focus of alignment will be at the anterior rectal wall at the level of the VUA (vesicoureteral anastomosis)
- Alignment to implanted fiducial markers may be used instead of daily CBCT
 - Weekly CBCT is strongly recommended to assess soft tissue anatomy and bladder and rectal filling.

Follow up

Disease monitoring	PSA every 3 months for first year and then every 6-12 months thereafter. First follow-up PSA should not be drawn sooner than 3 months post-radiation DRE if PSA is detectable and not actively declining
Androgen suppression monitoring (if applicable)	Bone density monitoring Consider repeating testosterone profile 6-12 months after initiating androgen suppression for men receiving long term therapy
Late toxicity evaluation	IPSS at each visit SHIM at each visit CTCAE assessed lower GI toxicity CTCAE assessed GU toxicity
Imaging	Not routinely indicated

Contributing authors

- [name], PhD (Site Leader)
- [name] (First Author)
- M. [name], PhD
- D. [name]
- [name]
- [name]
- [name], CMD
- [name], RT(R,T)
- [name], RT(R,T,CT)

References

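### Radiotherapy is not an attribution option and adverse events are not tabulated by treatment period, so the all-AE and all-SAE tables mix pelvic-radiotherapy and drug toxicity

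*Combined protocol and SAP*

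**What the plan says.** Section 8.3.6 frames causality around two agents: "In this study, there are 2 study drugs; the investigational drug Abemaciclib is given in combination with ADT". Each event is judged against each drug as a suspected reaction or as unrelated, the second category being defined as "Not Related: There is no reasonable possibility that the AE is associated with study drug". Radiotherapy is not among the things to which an event can be attributed.

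The collection window in section 8.3.2 has no break for the pause. "The AE reporting period for this study begins when the patient has received even a portion of the first dose of Abemaciclib study drug", and it "ends 28 days after the last dose of the latest study treatment". Section 10.2.2 then states: "All AEs with an onset after initiation of treatment will be considered as treatment-emergent AEs".

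The summaries listed in section 10.2.2 are all AEs, all SAEs, AEs related to abemaciclib, AEs leading to drug discontinuation, and clinically significant laboratory abnormalities, plus patient listings with attribution. None is by treatment period and none is for radiotherapy-related events. Section 10.2 bases the safety assessment on treatment-related events without saying whether radiotherapy counts as treatment.

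Radiotherapy is part of the schedule for every patient: 28 fractions to the whole pelvis with a prostate boost (section 4.1.2.2). Abemaciclib stops 2 weeks before it and resumes about 1 month after it (section 4.1.3, Table 2 footnotes b, g and h). ADT continues throughout.

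**The concern.** Tolerability and feasibility of abemaciclib with ADT is a secondary objective, and section 3 gives safety and tolerability as the purpose of the study. The documents list bowel toxicity for both sources. Section 2.3.2 reports diarrhea in 86% of patients in abemaciclib breast cancer studies, and section 2.1 names bowel complications as a risk of external beam radiotherapy. Section 2.4 adds that "CDK4/6 inhibition can act as a radiation sensitizer through its effects on the DNA damage response and interactions with cell cycle pathway proteins".

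With pelvic radiotherapy inserted between two blocks of abemaciclib, a reader will want to know what happened on abemaciclib before radiotherapy, during the pause, and on abemaciclib afterwards. No planned table shows this. If radiotherapy causality is not recorded when the event occurs, it is hard to recover reliably later.

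**Working it through.** The plan states no figure for this point, so the check sets the sections side by side and works out the length of the pause.

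**1. Start of radiotherapy.** Section 4.1.2.2 gives two and a half 28-day cycles first: 2.5 × 28 = 70 days. Adding the 14-day stop gives day 84, or 84 / 30.44 = 2.8 months, consistent with the stated 3 months.

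**2. Length of the pause.** Five fractions a week is an assumption; the documents give only the number of fractions.
- Low end: 14 days + 37 days from first to last fraction + 28 days = 79 days.
- High end: 14 days + (28 / 5) × 7 = 39.2 days + 30 days = 83.2 days.
- Share of 24 months (730 days): 79 / 730 = 10.8% and 83.2 / 730 = 11.4%.

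**3. Is abemaciclib still present when radiotherapy starts?** Section 2.3.2 gives a terminal half-life of 17 to 38 hours. Five half-lives are 5 × 17 = 85 h to 5 × 38 = 190 h, or 3.5 to 7.9 days, which is shorter than the 14-day stop. This covers the parent drug only. Section 6.7 mentions major circulating metabolites, and their half-lives are not given.

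**4. Route of a bowel event with onset during radiotherapy.**
- It falls inside the reporting period of section 8.3.2.
- It is treatment-emergent under section 10.2.2, so it enters the all-AE table and, if serious, the all-SAE table.
- It can be classed as unrelated to both drugs, and then does not enter the abemaciclib-related table.
- Nothing records that radiotherapy was the suspected cause. In the unrelated category it sits beside intercurrent illness.

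**5. The same event after abemaciclib restarts.** Section 8.3.9 has every rise or fall in grade entered as a new adverse event. A radiotherapy bowel event that changes grade after restart, even for the better, therefore becomes a new record with an on-drug onset date. Timing then no longer separates the two causes.

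**6. Illustration of the mixing.** The documents give no radiotherapy event rate, so these inputs are assumptions. If a proportion d of patients has a drug-caused grade 3 or higher event and an independent proportion q has one caused by radiotherapy, the all-cause proportion is 1 − (1 − d)(1 − q).
- d = q = 10%: 1 − 0.9 × 0.9 = 19%, or 5.7 of 30 patients against 3.0 from the drug alone.
- d = 5%, q = 2%: 6.9%.
- d = 20%, q = 20%: 36%.

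The abemaciclib-related table does not move if the radiotherapy events are judged unrelated.

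**The case against.** The strongest reply is that all-cause tables are meant to mix causes, and that the plan already offers ways to separate them. The unrelated category exists, section 10.2.2 has an abemaciclib-related summary and attribution listings, and section 8.1 says safety will be characterized by timing as well as incidence and relatedness. Onset and dosing dates would allow a split later, and section 10.2.2 leaves room for further exploratory analysis. All of this stands, and it limits the point. It does not supply a radiotherapy attribution or a prespecified period table.

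The effect on some rows may also be small. If the 86% diarrhea figure carried over to these patients, 0.86 × 30 = 25.8 would have the event from the drug alone, leaving about 4 of 30 who could newly enter the any-grade row. The abemaciclib profile in sections 2.3.2 and 2.6.1 lists no urinary toxicity, and events are coded by organ class and preferred term, so bladder events are easier to tell apart. The real overlap is in bowel events. Thirty patients are reached only if the null is rejected; otherwise the trial ends with 23 or 5.

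A reader might infer that events can be attributed only to abemaciclib or ADT, or that the abemaciclib rate must be inflated. The documents do not support either, because an event may be judged unrelated to both drugs. A reader might also infer that the trial ignores bowel grading. All AEs are graded by CTCAE 4.03, and the Appendix 3 entry "CTCAE assessed lower GI toxicity" belongs to late-toxicity follow-up, so it would not supply acute grades for the radiotherapy period.

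**Conclusion.** The point holds as a reporting gap. The all-AE and all-SAE tables combine drug toxicity with radiotherapy toxicity arising in a pause of about 79 to 83 days, roughly 11% of 24 months, assuming five fractions a week. Separation by cause rests on open-label, single-arm judgement with no radiotherapy option, and that judgement is weakest for bowel events after abemaciclib restarts.

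It would go too far to say that tolerability of the combination cannot be read, since the abemaciclib-related summary and the listings remain usable. The documents also do not support a count of patients affected, because they give no radiotherapy event rate. Nor can every event in the pause be assigned to radiotherapy, since ADT continues. Radiosensitization is offered as an efficacy rationale; a recall effect on restart is not mentioned anywhere and would be the reader's own inference. The primary endpoint and the two-stage decision rule are untouched.

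**What to change.** - **Section 8.3.6 and the AE form:** add radiotherapy as a third attribution, with the same two categories (suspected or not related) as for each drug.
- **Section 10.2.2:** add a table of AEs by onset period, with patients at risk and preferably person-time in each: (1) first abemaciclib dose to last abemaciclib dose before radiotherapy; (2) after that dose to abemaciclib restart, showing the 2-week stop before radiotherapy separately from radiotherapy start onward; (3) restart to the end of the AE reporting period. Keep the overall tables.
- **Grade changes:** because section 8.3.9 makes each one a new record, state whether a record that continues an earlier event is counted by its own date or by first onset.

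The cost is one form field and one table built from dates the trial must hold anyway. Treatment, sample size and the primary analysis do not change. Denominators per period will be small. The comparison before and after radiotherapy should be labelled descriptive, because dropout, dose reduction and exposure time differ between periods.

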8.3.7. Expectedness

All AEs and ADRs are considered “unexpected” if not listed in the Abemaciclib IB. For example, under this definition, hepatic necrosis would be unexpected (by virtue of greater severity) if the IB referred only to elevated hepatic enzymes or hepatitis. Similarly, cerebral thromboembolism and cerebral vasculitis would be unexpected (by virtue of greater specificity) if the IB listed only cerebral vascular accidents. “Unexpected,” as used in this definition, also refers to AEs or suspected ADRs that are mentioned in the IB as occurring with a class of drugs or as anticipated from the pharmacological properties of the drug, but are not specifically mentioned as occurring with the particular drug under investigation.

8.3.8. Exposure in Utero

If the partner of a study patient becomes or is found to be pregnant during the study or within 90 days of discontinuing the investigational medication/product, the Investigator must report the information to ELI LILLY, or designee via the Pregnancy Notification Report Form within 24 hours of awareness of the pregnancy. This must be done irrespective of whether an AE has occurred. The information submitted should include the anticipated date of delivery.

The Investigator will follow the pregnant partner of a study patient until completion of the pregnancy or until pregnancy termination (i.e., induced abortion) and then notify ELI LILLY, or its designee, of the outcome within 5 days or as specified below. The Investigator will provide this information as a follow-up to the initial report. The reason(s) for an induced abortion must be specified.

The Investigator should follow procedures for reporting an SAE if pregnancy outcome meets criteria for an SAE (e.g., spontaneous abortion, stillbirth, neonatal death, or congenital anomaly [including that in an aborted fetus]).

In the case of a live birth, the “normality” of the newborn can be assessed at the time of birth and the Pregnancy Outcome Report Form should be completed (i.e., no minimum follow-up period of a presumably normal infant must pass before a Pregnancy Outcome Report Form can be completed). The “normality” of an aborted fetus can be assessed by gross visual inspection unless pre-abortion laboratory findings are suggestive of a congenital anomaly.

Additional information about pregnancy outcomes that are classified as SAEs follows:

- “Spontaneous abortion” includes miscarriage and missed abortion.
- All neonatal deaths that occur within 1 month of birth should be reported, without regard to causality, as SAEs. In addition, any infant death after 1 month that the

Investigator assesses as possibly related to the *in utero* exposure to the study drug should also be reported.

8.3.9. Follow-up of Unresolved Adverse Events

All AEs should be followed until resolved, improved to the patient's pre-treatment baseline severity or better, or the patient's participation in the study is completed, whichever occurs first. All serious adverse events and those non-serious events assessed by the Investigator as suspected reactions (i.e., at least possibly related) to Abemaciclib must be followed, even after the patient's withdrawal from study, until the event is either resolved, improved to the patient's pre-treatment baseline or better, stable without anticipated future change, or the patient is lost to follow-up, or, in the case of a suspected adverse reaction, later determined to be not related to the ELI LILLY investigational medicinal product. Any increase or decrease in AE grade should be recorded as a new adverse event. All AEs should also be documented on the AE CRF.

